2.3 Study Scheme Diagram

3. Subject Selection

3.1 Number of Subjects and Subject Selection

All patients admitted to ITU with a length of stay of 5 or more days, fitting the study inclusion criteria, will be approached to participate in the study. The number of patients we aim to recruit to the study is 400 over a two month data collection period, in the ITUs of all Welsh hospitals. (Over a two month period in Morriston Hospital alone, there were over 100 patients with an ITU length of stay of 5 or more days). This allows for loss to follow up and non-response to the survey.

3.2 Inclusion Criteria

- Aged 18 years or more
- Capacity to consent to participation
- Capacity to complete survey
- ITU stay of five or more days
- Survived to three months post ITU discharge

3.3 Exclusion Criteria

- Aged less than 18 years
- No capacity to consent to participation
- No capacity to complete survey
- ITU stay of less than five days
- Does not survive to three months post ITU discharge
- Patients requiring chemotherapy that will potentially cause alopecia
- Patients who suffer with any pre-existing alopecia requiring dermatology input
- Patients who suffer with complete baldness

3.4 Criteria for Premature Withdrawal

- Death
- Patient request for study withdrawal

4. Study Procedures

4.1 Informed Consent Procedures

Consent will be obtained for participation in the study when the patient is awake / conscious and able to provide informed consent. Informed consent will be obtained by the chief or principal investigators who will all receive 'protocol and informed consent specific training' in alignment with the principles of GCP. Consent will be obtained following a full introduction to the study and once the patient has had time to discuss the Patient Information Sheet with a family member / carer (as appropriate). The participants will be given 24 hours to consider participation. A study withdrawal letter will also be attached to the Patient Information Sheet in case the patient wishes to withdraw consent at a later date.

4.2 Screening Procedures

All patients admitted to ITU with a length of stay of 5 or more days, fitting the study inclusion criteria, will be screened for potential participation in the study, by the chief or principal investigators. A screening log will be maintained throughout the study period.

4.6 Follow up Procedures (if applicable)

At three months post-ITU discharge, the patient will be sent a survey in the post. If there is no reply to the postal survey after one month, the CI / PI will contact that patient and administer the survey by telephone.

4.9 End of Study Definition

The study will end when all data has been collected and all surveys are completed. A six month period following end of patient recruitment will be used for completion of the second CRF and data cleaning / validation

4.11 Subject Withdrawal

A patient can withdraw from the study at any time during the data collection period. They will have a study withdrawal letter that can be sent to the CI at any time.

4.11 Data Collection and Follow up for Withdrawn Subjects

Any patient who withdraws consent will have their data removed from the study.

6. Safety Reporting

As this is a non-interventional study, there are no safety reporting issues to consider

7. Statistical Considerations

7.1 Primary Endpoint Efficacy Analysis

Patient reported alopecia as measured by a pre-designed survey

7.2 Secondary Endpoint Efficacy Analysis

Patient reported alopecia as measured by a pre-designed survey

7.3 Safety Endpoints

N/A

7.4 Sample Size

We aim to include sufficient patients in order that we can present the unadjusted and adjusted odds ratios and 95% confidence intervals for the risk factors for alopecia in survivors of critical illness. Vittinghoff and McCulloch (2007) suggested that the number of patients needed to ensure sufficient power in a cohort study is equivalent to five to nine events per variable (EPV) being investigated.(9) We will therefore use an EPV of 7 for this study. In this study we aim to investigate ten variables or risk factors therefore a minimum of 70 events (incidence of alopecia) were required. The previous pilot study completed by our research team reported an incidence of alopecia of 17% in survivors of critical illness, so we calculate that we need at least 400 patients in total. It would take two months to provide a sample of 400 patients (with a length of stay of 5 days to more) in the ITUs of all Welsh Hospitals, so we aim to recruit patients for four months to allow for mortality and loss to follow up.

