1.3 Clinical Data

In response to the work investigating alopecia in military survivors of critical illness(6), we undertook a small pilot study to investigate the incidence and nature of patient-reported alopecia in civilian survivors of critical illness. A total of 75 patients who had been discharged home for at least 12 weeks from our general ICU, attending the Follow-Up Clinic in 2014, completed a pre-designed alopecia survey. Median age was 65 years, with 35% males and a median ICU length of stay of eight days. A total of 17% of patients reported suffering alopecia. The severity of hair loss ranged between less than 10% to over 50%, with the location of hair loss varying between the patients. Duration of alopecia lasted between three weeks to seven months. The type of hair loss varied between patients, with only one patient reporting the additional loss of non-scalp hair. Five patients reported that complete regrowth had not occurred by the time they attended the clinic. There were no significant differences in demographic variables between the patients with and without alopecia.

The percentage of patients reporting alopecia was lower (17% versus 35%) than that reported by Scott et al (2014).(6) This could be due to the higher injury severity and longer median length of stay reported in the military cohort. The military cohort was also younger and all patients male, so further research into age and sex as risk factors for alopecia may be warranted. On analysis, no significant differences were found between the patients with and without alopecia in terms of age, sex, primary admission diagnosis and APACHE II score.

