2.2 Trial Design

Mixed methodology study: Prospective observational and qualitative methods

Setting and sample

The study will be multi-centred, led from Morriston Hospital. There is currently no standardised protocol used for the assessment and measurement of alopecia on our ITU. All patients who survive their admission to ITU, between June and October 2017 and have an ITU length of stay of 5 or more days will be included in this study.

Definition of variables

The risk factors under investigation are the following: APACHE II score, age, primary admission diagnosis, fever, mechanical ventilation days, length of stay, sepsis, all relevant medications (known to cause alopecia), or transfusions during the ITU stay. This information will be collected prospectively during the patient's ITU stay. The Acute Physiology and Chronic Health Evaluation (APACHE II) score is used to predict mortality in ICU patients. The diagnosis of severe sepsis will be given using the definition provided by the 'Surviving Sepsis Campaign' (2008). Patients' primary admission diagnoses will be classified as either surgical (including abdominal, maxilla-facial, spinal, vascular conditions), general medical (including renal, oncology, respiratory conditions), neurological (acute and chronic) and trauma. 'Mechanical ventilation days' will be defined as the number of days the patient required invasive mechanical ventilation. ITU length of stay will be defined as the number of whole days the patient was managed on ITU or the high dependency unit (HDU).

Study design

In order to address both aims of this study a mixed methods approach will be used. An observational design for the prospective data collection and analysis of potential risk factors will be used, with a survey design for the survey completion. The patients recruited in the prospective study will be used for the questionnaire stage of the study, in order that the risk factors for alopecia can be investigated.

Prospective study: Data will be collected for all patients who survive an ITU length of stay of five or more days. Data will be recorded on a pre-designed spreadsheet and each patient will be allocated a study number.

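### Sections 3.1 and 7.4 contradict each other on whether the 400 patients include or exclude losses, and no loss rate is stated, so the 70 events behind the risk-factor model cannot be verified.

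*Protocol*

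**What the plan says.** Section 7.4 builds the sample size on events per variable (EPV). It cites a range of five to nine and settles on one value: "We will therefore use an EPV of 7 for this study". It continues: "we aim to investigate ten variables or risk factors therefore a minimum of 70 events (incidence of alopecia) were required". For the event rate it says that the pilot "reported an incidence of alopecia of 17% in survivors of critical illness, so we calculate that we need at least 400 patients in total". It then says that two months would supply 400 patients with a long enough stay, "so we aim to recruit patients for four months to allow for mortality and loss to follow up". In this section 400 is the number needed, and the allowance for losses lies outside it.

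Section 3.1 reads differently: "The number of patients we aim to recruit to the study is 400 over a two month data collection period". After a parenthesis on patient numbers at the lead hospital it adds: "This allows for loss to follow up and non-response to the survey". Here 400 is the number recruited, and the allowance lies inside it.

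The synopsis gives 400 patients without saying whether they are recruited or analysed. Section 2.2 gives the inclusion window: "All patients who survive their admission to ITU, between June and October 2017". No section states a loss, mortality or survey response rate.

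**The concern.** The endpoint is alopecia reported by the patient on a survey sent three months after ITU discharge (Sections 2.1 and 4.6). A recruited patient who dies, withdraws or does not respond by post or telephone cannot be an observed event. Section 3.4 lists death and patient request as grounds for withdrawal, and Section 4.11 removes the data of anyone who withdraws consent. Whether 400 counts recruits or respondents therefore decides how many events to expect.

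The EPV argument is the protocol's only sample size justification. If Section 3.1 governs, the ten-variable logistic model rests on fewer events than Section 7.4 calls the minimum, by an amount that depends on a loss rate that nobody has written down. The likely consequences are less stable odds ratios, wider confidence intervals, and a published EPV of 7 that the study did not have.

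**Working it through.** **Inputs.** EPV 7, ten variables, 70 events and 17% incidence (Section 7.4). Pilot of 75 patients (Section 1.3); 17% of 75 implies 13 patients, since 13/75 = 17.3%. Loss rates are not in the protocol, so 10% to 50% is used as an assumed range.

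**The plan's own figure.** Events needed = 7 × 10 = 70. Patients needed = 70/0.17 = 411.8, rounded up to 412. The stated 400 is 12 lower, or 3% of 400, and gives 400 × 0.17 = 68 expected events (EPV 6.8). With the unrounded pilot rate, 70/(13/75) = 403.8, rounded up to 404, and 400 patients give 400 × 13/75 = 69.3 events. So 400 is close to the protocol's own result, but slightly under its stated minimum at either rate.

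**Section 3.1 reading: 400 recruited, losses inside.** With loss d, expected events = 400 × (1 − d) × 0.17, and EPV = events/10. The last column gives the recruits needed for 412 respondents, 412/(1 − d), rounded up.

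| Assumed loss d | Respondents | Expected events | EPV | Recruits for 412 respondents |
|---|---|---|---|---|
| 0% | 400 | 68.0 | 6.8 | 412 |
| 10% | 360 | 61.2 | 6.1 | 458 |
| 20% | 320 | 54.4 | 5.4 | 515 |
| 30% | 280 | 47.6 | 4.8 | 589 |
| 40% | 240 | 40.8 | 4.1 | 687 |
| 50% | 200 | 34.0 | 3.4 | 824 |

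EPV reaches the cited lower bound of 5 at 50 events: 1 − 50/68 = 0.265, a loss of about 26%.

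These are expectations. The binomial probability of 70 or more events at 17% is 0.42 with 400 respondents, 0.12 with 360, 0.014 with 320 and 0.0004 with 280.

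**Section 7.4 reading: 400 needed, losses outside.** If two months supply 400 long-stay patients, four months supply about 2 × 400 = 800. Reaching 412 respondents then requires 412/800 = 51.5% of them to be eligible, consent, survive and respond. That may be attainable, but the protocol gives no figure to judge it by.

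**Recruitment period.** Two months (Section 3.1) conflicts with four (Section 7.4). June to October 2017 (Section 2.2) is about four to five months, which fits Section 7.4 and not Section 3.1.

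**The case against.** The strongest defence has five parts.

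- **412 against 400 is close to rounding.** This stands. 400 respondents give EPV 6.8, well inside the cited range, and the unrounded pilot rate gives 404. A pilot of 75 patients cannot separate 400 from 412. A reader might infer that the sample size fails on arithmetic; the protocol does not support that.
- **Sixty-eight is an expectation, not a ceiling.** This also stands. A reader might infer that 70 events cannot be reached, but with 400 respondents the chance is about 42%. It becomes small only at loss rates that have to be assumed. Equally, EPV does not simply leave the 5 to 9 range: at 20% loss it is 5.4. Telephone follow-up of postal non-responders (Sections 2.2 and 4.6) should limit the loss.
- **No rule stops recruitment at 400.** Correct. Section 3.1 states an aim, the synopsis a bare number, and Section 2.2 takes all qualifying patients in its window. That a site would stop at 400 is conjecture. Nor is Section 2.2 a third, conflicting window, since it fits the four months of Section 7.4.
- **The allowance in Section 3.1 may refer to the pool of available patients**, because it follows the parenthesis on numbers at the lead hospital. This is possible, but Section 3.1 still calls 400 the number recruited and still gives two months. Likewise, survival to three months is an inclusion criterion (Section 3.2), so deaths may not count against the 400; yet death is also a withdrawal criterion (Section 3.4), so the protocol leaves this open.
- **The primary objective is not endangered.** This stands. The 95% half-width for an incidence of 17%, 1.96 × √(0.17 × 0.83/n), is about 3.7 percentage points with 400 respondents and 4.8 with 240.

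What the defence does not remove is the conflict between Sections 3.1 and 7.4 and the absence of any loss rate.

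**Conclusion.** The point holds as an inconsistency. Section 7.4 treats 400 as the number needed, with four months of recruitment to absorb losses; Section 3.1 treats 400 as the number recruited in two months, with losses absorbed already. Under Section 3.1 the stated 70 events are not expected at any loss rate: 68 at zero loss, 54 at 20%, 48 at 30% and 41 at 40%. EPV is then below the chosen 7 throughout, and below the cited bound of 5 only if losses exceed about 26%. Under Section 7.4 about 70 events may be reached, but this cannot be checked.

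The sizes rest on 17% incidence, ten model variables and assumed loss rates. The 12-patient gap between 400 and 412 is a minor correction. Because EPV serves the secondary, risk-factor objective, this is something that should be fixed rather than a defect that undermines the study.

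**What to change.** In Section 7.4, state the target as patients with a postal or telephone survey result: 412 for 70 expected events at 17% and ten variables. State the assumed loss and non-response rate, and derive the number to recruit from it (for example 515 at an assumed 20% loss, 589 at 30%). Align Section 3.1 and the synopsis with the four-month period of Section 7.4, which the window in Section 2.2 already fits, and say in each place whether the number counts recruits or respondents.

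Confirm the variable count at the same time, since 412 depends on it. Section 2.2 appears to list nine risk factors (9 × 7 = 63 events; 63/0.17 = 370.6, so 371 patients), while admission diagnosis has four classes and would use three model parameters rather than one.

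If recruitment stays at 400, restate the expected events and EPV, for example 41 to 54 events at 60% to 80% response, and limit the risk-factor model to the parameters that this supports: 41/7 = 5.9 and 54/7 = 7.7, so about 5 to 7 at EPV 7.

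The cost is protocol wording plus one of three things: a higher recruitment target, a less favourable stated EPV, or a smaller model.

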7.5 Statistical Analysis

Results will be presented descriptively using numbers and percentages (categorical data) or median and interquartile ranges (continuous data). Risk factors will be analysed using Fisher's Exact test and multivariable logistic regression on SPSS (Chicago, Version 22). Missing data will be handled in the final analysis using a multiple imputation system.

8. Data Handling & Record Keeping

8.1 Confidentiality

The CI will take responsibility to ensure that patient anonymity is protected and maintained. The CI will also ensure that their identities are protected from any unauthorised parties. Information with regards to study patients will be kept confidential and managed in accordance with the Data Protection Act, NHS Caldicott Guardian, The Research Governance Framework for Health and Social Care and Research Ethics Committee Approval.

All patients will be allocated a study number once informed consent is obtained. Personal data will only be identifiable by this study number during data collection. Data collection will only include the risk factors (as outlined earlier). All patient identifiable data will be removed and data completely anonymised once data collection using the survey is completed. Data will be stored on a Health Board, password encrypted computer, only accessible to the CI / PIs of the study team. The CI will act as the custodian of the data. The Caldicott Guidelines will be adhered to throughout the study.

8.2 Study Documents

A copy of the patient consent form, Patient Information Sheet, study withdrawal letter and case report form is attached to this submission. A Trial Management file will be used and all hard copies (as listed below), will be kept in a locked room within the physiotherapy department.

- A signed protocol and any subsequent amendments
- Sponsor Self-Monitoring template for the trial team to complete on a regular basis as detailed by the Monitoring section
- Current/Superseded Patient Information Sheets (as applicable)
- Current/Superseded Consent Forms (as applicable)
- Indemnity documentation from sponsor
- Conditions of Sponsorship from sponsor
- Conditional/Final R&D Approval
- Signed site agreement
- Ethics submissions/approvals/correspondence
- CVs of CI and site staff
- Delegation log
- Staff training log
- Site signature log
- Patient identification log
- Screening log
- Enrolment log
- Monitoring visit log
- Protocol training log
- Correspondence relating to the trial
- Communication Plan between the CI/PI and members of the study team

8.3 Case Report Form

A copy of the case report form is attached to this submission

8.4 Record Retention and Archiving

During the course of research, all records will be the responsibility of the Chief Investigator and will be kept in secure conditions. Once the research trial is complete, the records will be kept securely for a further 5 years in the Health Board archive facility.

8.5 Compliance

The CI will ensure that the trial is conducted in compliance with the principles of the Declaration of Helsinki (1996), and in accordance with all applicable regulatory requirements including but not limited to the Research Governance Framework, Trust and Research Office policies and procedures and any subsequent amendments.

8.6 Clinical Governance Issues

8.6.1 Ethical Considerations

This protocol and any subsequent amendments, along with any accompanying material provided to the patient in addition to any advertising material will be submitted by the Investigator to an Independent Research Ethics Committee. Written Approval from the Committee must be obtained and subsequently submitted to the Research & Development Department to obtain Final R&D approval.

8.7 Quality Control and Quality Assurance

8.7.1 Summary Monitoring Plan

The Research Governance Manager will monitor this study in accordance with Health Board Policy

8.7.2 Audit and Inspection

Auditing: Definition "A systematic and independent examination of trial related activities and documents to determine whether the evaluated trial related activities were conducted, and the data were recorded, analysed and accurately reported according to the protocol, sponsor's standard operating procedures (SOPs), Good Clinical Practice (GCP), and the applicable regulatory requirement(s)."

This study may be identified for audit by any method listed below:

1. A project may be identified via the risk assessment process.

2. An individual investigator or department may request an audit.

3. A project may be identified via an allegation of research misconduct or fraud or a suspected breach of regulations.

4. Projects may be selected at random. The Department of Health states that Trusts should be auditing a minimum of 10% of all research projects.

5. Projects may be randomly selected for audit by an external organisation.

Internal audits will be conducted by a sponsor's representative

Appendix 1 – Information with regards to Safety Reporting in Non-CTIMP Research

	Who	When	How	To Whom
SAE	Chief Investigator	-Report to Sponsor within 24 hours of learning of the event -Report to the MREC within 15 days of learning of the event	SAE Report form for Non-CTIMPs, available from NRES website.	Sponsor and MREC
Urgent Safety Measures	Chief Investigator	Contact the Sponsor and MREC Immediately Within 3 days	By phone	Main REC and Sponsor
			Substantial amendment form giving notice in writing setting out the reasons for the urgent safety measures and the plan for future action.	Main REC with a copy also sent to the sponsor. The MREC will acknowledge this within 30 days of receipt.
Progress Reports	Chief Investigator	Annually (starting 12 months after the date of favourable opinion)	Annual Progress Report Form (non- CTIMPs) available from the NRES website	Main REC
Declaration of the conclusion or early termination of the study	Chief Investigator	Within 90 days (conclusion) Within 15 days (early termination) The end of study should be defined in the protocol	End of Study Declaration form available from the NRES website	Main REC with a copy to be sent to the sponsor
Summary of final Report	Chief Investigator	Within one year of conclusion of the Research	No Standard Format However, the following Information should be included:- Where the study has met its objectives, the main findings and arrangements for publication or dissemination including feedback to participants	Main REC with a copy to be sent to the sponsor
